11.4.3 Pregnancy

In the case of pregnancy occurring during trial treatment, the investigator must report it to the SAKK by completing the SAKK pregnancy reporting form. This form (available on the SAKK portal, Trials → SAKK 41/13-Aspirin → CRFs) has to be filled in immediately and faxed to the SAKK CC. The investigator shall ensure that the case is followed-up to the end of the pregnancy and supply a final report on the outcome to the SAKK CC. In addition, the investigator has to report any fetal anomaly, stillbirth or any other medicinal significant event concerning the pregnancy as SAE (see above 11.4.1 and 11.4.2).

11.5 Procedure for reporting individual SAEs by the investigator

Any SAE must be reported by submitting the completed **initial report section** of the trial-specific SAE form within **24 hours** of becoming aware of the event. This form can be downloaded from the SAKK portal (portal.sakk.ch → Trials → SAKK 41/13-Aspirin → CRFs).

Submission is done by sending the SAE form by email to: [contact].

The SAE outcome must be reported within 2 weeks after initial report by submitting the **follow-up** report (e.g. initial SAE form, updated with follow-up information) to the SAKK CC as above. In case the SAE is reported as ongoing after 14 days, the follow-up report has to be submitted again with the final outcome.

The originals of the SAE forms (both initial and follow-up reports) are kept at the sites in the investigator's file. The SAKK CC will forward each individual SAE to the coordinating investigator and to Bayer.

11.6 Reporting of individual SAEs and SUSARs by the sponsor

The SAKK CC ensures that all reporting requirements and timelines for reporting, as defined in the respective applicable national and international laws, are followed.

The SAKK CC will forward any SAE which is fatal and occurred at a Swiss site to the lead EC according to the Swiss HRA and its applicable ordinances.

The SAKK CC will report every SUSAR to all principal investigators, to the involved ECs, to Swissmedic and/or to the competent authorities of foreign countries (unless specified otherwise in the contract with a foreign site or foreign contract research organization (CRO), as specified in the Swiss HRA and the EU Clinical Directive 2001/20/EC. SUSARs occurring within CH or the EU will be entered into the Eudravigilance database by SAKK Safety Office within the required timeframe.

Additionally, SAKK CC will report SUSARs to Bayer.

11.7 Reporting of safety signals

In case the investigator receives external safety reports/letters related to the IMP, he/she must report to the sponsor within 7 days. The SAKK CC will forward these reports/letters to all investigators and to the local and lead ECs if applicable.

11.8 Periodic reporting on safety to principal investigators and regulatory authorities

The SAKK CC ensures that the reporting requirements and timelines for reporting, as defined in the respective applicable laws, are followed.

A yearly Data Safety Update Report (DSUR) will be provided to the local investigators for filing in the investigator's file. The SAKK CC will submit the DSUR to the involved ECs, to Swissmedic, to the competent authorities of foreign countries and to Bayer. Since the trial has been closed in the foreign countries in Q3 2021 without further follow-up, the DSUR will be replaced by an Annual Safety Report (ASR) and will be submitted from 2022 onwards only to the Swiss local investigators, competent authorities, ECs and to Bayer.

12 EVALUATIONS AND INVESTIGATIONS BEFORE, DURING AND AFTER TRIAL TREATMENT

All assessments and investigations must be done within the defined time as indicated below.

An adaptable Excel schedule of assessments can be downloaded from the SAKK portal (portal.sakk.ch → Trials → SAKK 41/13-Aspirin → Documents → schedule of assessments).

12.1 Pretreatment evaluations and procedures

Informed consent for trial entry must be obtained before inclusion of the patient into the trial and prior to any trial-specific procedures (with the exception of the separately consented PIK3CA mutation analysis). Informed consent for PIK3CA mutation testing is obtained separately from and prior to the consent for trial entry.

Complete resection (R0) of the primary tumor must have been performed (max. 14 weeks prior to trial entry).

Stage II (pT3/T4 N0 cM0) or stage III (pTx pN+ cM0) and histologically diagnosis of adenocarcinoma of the colon must have been confirmed.

12.1.1 The following investigations have to be performed within 14 weeks before registration:

- Central PIK3CA mutation analysis (see section 17.1 for details on required material and logistics)

12.1.2 The following investigations have to be performed within 28 days before or on registration:

- Documentation of information on the patient, including ethnicity and risk factors
- Documentation of medical history, including baseline symptoms, surgical therapy, pre-surgery CEA, tumor history and location
- Physical examination, including assessment of WHO PS, weight and height
- Hematological values: hemoglobin, platelets
- Renal function: serum creatinine, calculated creatinine clearance (according to the formula of Cockcroft-Gault, see Appendix 2)
- Hepatic function: total bilirubin, ALT, AST, AP
- Pregnancy test for women with child-bearing potential (**within 7 days** prior randomization)
- Post-resection CEA level
- Assessment of all inclusion/exclusion criteria

Only for patients who consented to translational research:

- 5 ml EDTA-blood sample (see section 18.2 for details)

12.2 Evaluations during trial treatment

Trial treatment must start within 14 days following randomization.

OF NOTE: the time points of investigations and assessments refer to the date of surgery and not the date when the patient was randomized into the trial.

As such, the schedule of evaluations during the treatment and follow-up phases of the trial is according to the guidelines from the Swiss Association for Gastroenterology (SGG/SSG) & European Society of Medical Oncology (ESMO) for the follow-up of patients with colon cancer [24, 25]. Based on the recommendations of ESMO, clinical examinations and CEA measurements will be performed every 3 months during the first 24 months of evaluation as the vast majority of recurrences occur during the first 2 years after removal of the primary tumor. These examinations and any additional investigation upon suspected recurrence are not subjected to any limitation.

Table 2 below illustrates the time points of assessments in reference to the date of surgery versus the schedule of trial treatment.

Table 2: summary of assessments

Trial phase	Adjuvant aspirin/placebo daily**												Follow-up		
	3	6	9	12	15	18	21	24	30	36	42	48	54	60	
Month after surgery*															
Clinical examination and CEA level	x	x	x	x	x	x	x	x	x	x	x	x	x	x	x
AEs	x	x	x	x	x	x	x	x	x	x					
Colonoscopy				x								x			
CT scan chest/abdomen				x				x		x		x		x	

*Starting time point is date of colon cancer resection

**Adjuvant aspirin/placebo treatment is initiated within max. 16 weeks after colon cancer resection and is administered for 3 years from treatment start (or until tumor recurrence, death, patient refusal or withdrawal by the physician, whichever occurs first)

12.2.1 Year 1 and 2 following surgery

- Assessments to be done at 3*, 6, 9, 12, 15, 18, 21 and 24 months [± 2 weeks]
 - Clinical examination
 - Signs and symptoms of bleeding disorders, including but not limited to: gastrointestinal hemorrhage with loss of fresh blood per rectum, intracranial hemorrhage
 - Laboratory investigations (e.g. hemoglobin, platelets) only if clinically indicated
 - CEA level

In case of significant increase compared to baseline (post-surgery): recurrence must be confirmed by colonoscopy or CT scan or other imaging technique
 - AEs (only while patient is under trial treatment)

Only report AEs grade ≥ 3 potentially related to trial medication
 - Verify patient diary (i.e. patient's compliance to the protocol treatment & patient's intake of acetylsalicylic acid or other NSAIDs or COX-2 inhibitors beside trial treatment)
 - Collect information on concomitant anti-tumor adjuvant chemotherapy (e.g. regimen (doublet or monotherapy) versus no adjuvant chemotherapy, start/end date, etc.)

*) Note: If a patient is included into the trial later than three months after surgery, the visit at 3 months is omitted (and the first trial visit during treatment will take place 6 months after surgery).

- Assessments to be done at 12 and 24 months [± 2 weeks]
 - CT scan chest/abdomen (oral and i.v. contrast strongly recommended)
- Assessments to be done at 12 months [± 2 weeks]
 - Colonoscopy

12.2.2 Year 3 following surgery

- Assessments to be done at 30 and 36* months [± 1 month]
 - Clinical examination
 - Signs and symptoms of bleeding disorders, including but not limited to: gastrointestinal hemorrhage with loss of fresh blood per rectum, intracranial hemorrhage
 - Laboratory investigations (e.g. hemoglobin, platelets) only if clinically indicated
 - CEA level

In case of significant increase compared to baseline (post-surgery): recurrence must be confirmed by colonoscopy or CT scan or other imaging technique
 - AEs (only while patient is under trial treatment)

Only report AEs grade ≥ 3 potentially related to trial medication

- Verify patient diary (i.e. patient's compliance to the protocol treatment & patient's intake of acetylsalicylic acid or other NSAIDs or COX-2 inhibitors beside trial treatment)*
*) Note: If a patient is still under trial treatment at month 36, the last patient diary verification will have to be done during the first follow-up visit at month 42.
- Assessments to be done at 36 months [\pm 1 month]
 - CT scan chest/abdomen (oral and i.v. contrast strongly recommended)

12.3 Evaluations in the follow-up phase

All patients randomized in Swiss sites will be followed-up for at least 3 years from the date of surgery (or until death, whichever occurs first), until the last patient completes the 3 years of follow-up from the date of surgery, which is expected in Q3 2024. The follow-up of patients randomized in non-Swiss sites was prematurely stopped in Q2 2021.

Evaluations in the follow-up phase will be different for disease-free patients and patients who experienced recurrence.

After a patient experienced recurrence, further treatment and investigation is up to the treating physician.

12.3.1 Patients without recurrence

Patients who completed trial treatment as per protocol (i.e. 3 years of treatment; for patients who stopped trial treatment earlier because of closure by the sponsor, please follow the instructions below under “Patients without recurrence who were transferred to the follow-up phase before completion of trial treatment”):

- Bi-yearly assessments at 42*, 48, 54, and 60 months after surgery [\pm 1 month]
 - *) Note: If a patient is still under trial treatment at month 36, the last patient diary verification will have to be done during the first follow-up visit at month 42 (see section 12.2.2).
 - Clinical examination
 - CEA level
 - In case of significant increase compared to baseline (post-surgery)*: recurrence must be confirmed by colonoscopy or CT scan or other imaging technique
 - Patient's intake of acetylsalicylic acid or other NSAIDs or COX-2 inhibitors
- Yearly assessments at 48 and 60 months after surgery [\pm 1 month]
 - CT scan chest/abdomen (oral and i.v. contrast strongly recommended)
- At 48 months only [\pm 1 month]
 - Colonoscopy
- From year 6 to 10 after surgery (yearly assessments at months 72, 84, 96, 108 and 120 after surgery [\pm 2 months])
 - Disease and survival status
 - Patient's intake of acetylsalicylic acid or other NSAIDs or COX-2 inhibitors

This is performed with a phone call to the primary care physician.

Patients without recurrence who were transferred to the follow-up phase before completion of trial treatment (i.e. before 3 years of aspirin or placebo administration):

- Until and including year 3 (i.e. until 36 months after surgery)
 - Patients will be evaluated according to the schedule of assessments as described in section 12.2, with the exception of AEs and signs or symptoms of bleeding disorders (which do not need to be assessed)
- Bi-yearly assessments at 42, 48, 54, and 60 months after surgery [\pm 1 month]
 - Assessments as defined above

- From year 6 to 10 after surgery (yearly assessments at months 72, 84, 96, 108 and 120 after surgery [\pm 2 months])
 - Disease and survival status
 - Patient's intake of acetylsalicylic acid or other NSAIDs or COX-2 inhibitors

This is performed with a phone call to the primary care physician.

12.3.2 Patients after recurrence

- Every year for at least 3 years from the date of surgery
 - Survival status

This is performed with a phone call to the primary care physician.

13 CRITERIA OF EVALUATION AND DEFINITION OF ENDPOINTS

13.1 Criteria of evaluation

The populations used for analysis will include the following:

- Full analysis population: the full analysis population is defined as all randomized patients who received at least one dose of aspirin/placebo excluding patients with major eligibility violations. Following the intention-to-treat principle, patients in this population will be analyzed according to the treatment they were randomized to.
- Per protocol (PP) population: the PP population is based on the full analysis population excluding patients with major protocol violations. All decisions to exclude patients from the PP population must be made by the coordinating investigator together with the trial team prior to the analysis, blinded to the treatment arm and without looking at any efficacy data. Patients in this population will be analyzed according to the actual treatment they received.
- Safety population: the safety population is defined as all patients who received any dose of aspirin/placebo. Patients will be analyzed according to the actual treatment they received.

13.2 Definition of Endpoints

13.2.1 Primary endpoint

The primary endpoint of this trial is DFS, defined as time from surgery until one of the following events, whichever comes first:

- recurrence
- second cancer
- death due to any reason

Patients not experiencing an event will be censored at the date of the last available tumor assessment.

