Patients with resected colon cancer stage II or stage III bearing somatic mutations in exon 9 or 20 of PIK3CA will be 2:1 randomized to daily adjuvant aspirin 100 mg versus placebo for a maximum of 3 years or until disease recurrence, patient death or withdrawal of consent, whichever occurs first. Patients will be followed up for at least 3 years from the date of surgery.

The intake of aspirin or placebo is independent of adjuvant chemotherapy, and does not impact on the indication to give (or not to give) adjuvant chemotherapy.

MEASUREMENTS AND PROCEDURES

Following complete resection of their primary tumor, potentially eligible stage II or stage III colon cancer patients will undergo PIK3CA testing. Mutation screening will be performed centrally in archived formalin-fixed paraffin-embedded (FFPE) tumor tissue. Baseline assessments before trial treatment include clinical examination and blood testing for safety parameters and tumor marker. The trial therapy consists in daily aspirin (100 mg) or placebo *per os*.

The schedule of assessments during trial treatment and in the follow-up phase is in line with the guidelines from the Swiss Association for Gastroenterology (SGG/SSG) and the European Society of Medical Oncology (ESMO) for the follow-up of patients with colon cancer. Clinical examinations and carcinoembryonic antigen (CEA) measurements are to be performed every 3 months during the first 2 years following surgery, thereafter every 6 months until year 5. Bleeding-related adverse events potentially related to trial medication are to be recorded throughout trial treatment. Colonoscopy will be performed at year 1 and 4 following surgery, whereas computer tomography (CT) of the chest and abdomen are to be performed once a year. From year 6 to 10, disease and

survival status will be collected yearly. After recurrence, only survival status will be recorded for up to 10 years from surgery.

STATISTICAL CONSIDERATIONS

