9.4 Treatment duration

Patients will be transferred to the follow-up phase as soon as one of the following events occurs:

- treatment was completed as per protocol
- recurrence (must be confirmed by imaging)
- patient refusal (see 22.4 Premature withdrawal)
- withdrawal by the physician (see 22.4 Premature withdrawal)
- patient becomes pregnant
- premature trial closure by the sponsor (in Q4 2020, the sponsor decided to prematurely stop the accrual of the trial and the trial treatment due to financial reasons)

See section 12.3 for evaluations after treatment termination.

All patients randomized in Swiss sites will be followed-up for at least 3 years from the date of surgery. The follow-up of patients randomized in non-Swiss sites was prematurely stopped in Q2 2021.

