13.2.2 Secondary endpoints

Time to recurrence

TTR will be calculated from surgery until recurrence or death due to colon cancer. Patients not experiencing an event or patients who died due to other reasons before experiencing an event will be censored at the date of the last available tumor assessment.

Overall survival

OS will be calculated from surgery until death from any cause. Patients not experiencing an event will be censored at the last date they were known to be alive.

Cancer-specific survival

CSS will be calculated from surgery until death due to colon cancer, whether due to the original tumor or to a second primary same cancer. Patients who died due to other reasons will be censored at the time of death. All other patients will be censored at the last date they were known to be alive.

Adverse events

AEs will be assessed according to NCI CTCAE v4.0.

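### DFS and TTR are censored at an undefined last tumor assessment while events learned of by phone after month 60 still count, which can give a false aspirin median in supportive DFS and in TTR

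*Combined protocol and SAP*

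**What the plan says.** Section 13.2.1 defines DFS as time from surgery to recurrence, second cancer or death from any cause, with no upper time limit. Event-free patients are handled thus: "Patients not experiencing an event will be censored at the date of the last available tumor assessment". Section 13.2.2 uses this anchor for TTR and extends it to competing deaths: "patients who died due to other reasons before experiencing an event will be censored at the date of the last available tumor assessment". In the same section, OS and CSS are censored at the last date the patient was known to be alive, and for CSS "Patients who died due to other reasons will be censored at the time of death".

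Visits are quarterly for two years after surgery and "thereafter every 6 months until year 5" (section 1). Section 12.3.1 places the last examination, CEA and CT at month 60. From month 72 to month 120 it schedules one yearly contact on disease and survival status, made by phone to the primary care physician. On a CEA rise, section 12.2.1 says "recurrence must be confirmed by colonoscopy or CT scan or other imaging technique". Nowhere is tumor assessment defined.

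Section 15.3 asks for a Kaplan-Meier median with 95% CI per arm for each time-to-event endpoint. It censors unblinded patients, for the primary analysis, at the last tumor assessment before unblinding, and adds a supportive analysis that ignores unblinding. Section 7.5 dates the general unblinding to December 2020, for all patients.

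**The concern.** Events and censoring run on different clocks after month 60. A death, second cancer or recurrence learned of by phone enters at its date. A phone report that the patient is alive and disease-free adds no time at risk if the call is not a tumor assessment. That is the plain wording, because the OS and CSS definitions show that the authors had a contact-based anchor available and did not use it for DFS or TTR.

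Event-free patients therefore leave the risk set by about month 61, and those who remain are almost all patients who will have an event. The estimated curve then collapses for a reason unrelated to prognosis. The aspirin arm suffers most, because its expected median lies well beyond follow-up and should normally be reported as not reached. At stake is a descriptive result, the median and the tail of the curve.

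**Working it through.** **Inputs from the protocol.** 3-year DFS 70% (placebo) and 85% (aspirin), constant hazards, HR 0.456 (15.1); 113 patients randomized 2:1 (4.1.1); first patient Q2 2016 (section 1); surgery at most 14 weeks before registration (6.1.6); general unblinding December 2020 (7.5); foreign follow-up stopped Q2 2021 (section 5); end of Swiss follow-up Q4 2023 (sections 1 and 5) or Q3 2024 (12.3).

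**Reproducing the design figures.**
- HR = ln(0.85)/ln(0.70) = 0.456, as stated.
- Hazards: -ln(0.85)/3 = 0.0542 and -ln(0.70)/3 = 0.1189 per year.
- Medians: ln 2/0.0542 = 12.8 years (aspirin) and ln 2/0.1189 = 5.8 years (placebo).
- Aspirin DFS at month 60: S(60) = 0.85^(60/36) = 0.763.

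**Closed form.** With k late events, and m event-free patients who have a tumor assessment after the last of them, the curve ends at S(60) × m/(m+k). For k = 1:

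| m | End of aspirin curve | Median reported? |
|---|---|---|
| 0 | 0 | yes, false |
| 1 | 0.763 × 1/2 = 0.38 | yes, false |
| 2 | 0.763 × 2/3 = 0.51 | no |

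**Which analyses reach the phone period.** The earliest possible surgery is 1 April 2016 minus 14 weeks, which is 25 December 2015.
- To 31 December 2020 is 60.2 months. Primary DFS, cut at unblinding, stops before any call.
- To 30 June 2021 is 66.2 months. The first call is due at month 72 ± 2, so no foreign patient reaches one.
- Swiss patients followed to Q4 2023 or later can reach calls. They enter supportive DFS, and also TTR if the unblinding rule does not apply to it.

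**How often.** The documents give neither the Swiss share nor the hazard after month 60, so both are assumed over a range. The simulation used 75 aspirin and 38 placebo patients, uniform registration from April 2016 to December 2020, surgery 4-14 weeks earlier, 20% lost per 3 years, protocol visit windows, and design hazards to month 60. Events known at an attended visit or call count at their date. All other patients are censored at the last examination visit. For Swiss share 25-75% and end of follow-up Q4 2023:

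| Hazard after month 60 | False aspirin median, as written | Same, if calls count for censoring |
|---|---|---|
| 10-25% of design | about 4-18% of trials | about 0.4-2.5% |
| 100% of design | about 24-56% | about 6-10% |

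The lower hazards fit section 12.2 better, which says that "the vast majority of recurrences occur during the first 2 years after removal of the primary tumor".

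**Given a late event.** With at least one aspirin event in the phone period, the false median appears in 95-100% of simulated trials. If 10% of event-free patients followed past month 60 have an unscheduled scan, this falls to 75-92%; with 20% scanned, to 47-82%. These conditional figures come from runs whose upper end assumes a Swiss share of 100%.

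**Hazard ratio.** An event whose risk set contains only that patient contributes exp(βx)/exp(βx) = 1 to the Cox partial likelihood, hence no information. In simulation the HR moves by at most 0.02. The placebo DFS median moves by at most about 0.2 year, since it is expected near 5.8 years in any case.

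**The case against.** The strongest reply is that the call may be meant as a tumor assessment. Section 12.3.1 lists the year 6-10 contacts as yearly assessments and they record disease status. On that reading the problem disappears. The imaging requirements in 9.4 and 12.2.1 do not settle it: they say how a recurrence is confirmed, not that a disease-free report is no assessment. This stands as far as the wording goes. The contrast with the OS and CSS anchors still favours the narrower reading, and a term that decides the censoring date should not need inference. Section 15.3 defers full details to a SAP. The text available here contains no definition, though one may exist there.

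Three further points stand in part. Late scans are possible, since section 12.2 says "These examinations and any additional investigation upon suspected recurrence are not subjected to any limitation", and two of them prevent the false median after a single event. Section 15.3 requires a median per endpoint and does not clearly require one for the supportive analysis. Its unblinding rule could also be read to cover TTR. High simulated frequencies need a Swiss share near 100%, which conflicts with the foreign-site patients described in sections 5, 9.4 and 12.3.

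A reader might infer that the primary result is compromised. The documents do not support that. Primary DFS is cut at no more than 60.2 months if the general unblinding triggers the rule in 15.3, and the HR barely moves. A reader might also infer that a collapsed curve is the expected outcome. That holds only given a late event and few later scans, and the chance of a late event depends on figures the protocol does not give.

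**Conclusion.** The point holds as a minor descriptive error. On the plain wording of 13.2, one aspirin event learned of after month 60 can take the curve from 0.763 to 0 (0.38 with one later scan among event-free patients, 0.51 with two). The resulting median of about 5.5-6 years compares with 12.8 years under the design hazard. The arithmetic is certain given the reading; the frequency is not. It is roughly 4-18% of trials at late hazards of 10-25% of design and 24-56% at full design hazard, assuming a Swiss share of 25-75% and follow-up to Q4 2023. Unscheduled scans lower these figures; events learned of between calls would raise them.

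The finding is confined to supportive DFS, if it reports a median or the late curve, and to TTR, if the unblinding rule does not reach it. Confidence is medium because the premise rests on one reading of an undefined term.

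**What to change.** **In 13.2, for DFS and TTR:** censor event-free patients at the last date known to be disease-free, and state that the year 6-10 disease-status contact counts. Keep all deaths and other events as now defined. Do not add a clause that counts events only up to the last completed visit: a patient who dies at month 14 has a last visit at month 12, so such a clause would drop early deaths from primary DFS. For TTR, censor other-cause deaths at the date of death, as CSS does.

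**Alternative, for supportive DFS and TTR only:** cut both events and censoring at month 60.

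**In 15.3:** state that the December 2020 general unblinding triggers the censoring rule, and whether the rule applies to TTR. This matters because section 7.5 tells sites not to record that unblinding on the unblinding form, so a flag derived from the form would miss it.

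**Cost:** a few sentences and no new data. Phone status is less sensitive than CT. Small late risk sets can still give an unstable median: about 0.4-2.5% of trials at late hazards of 10-25% of design and 6-10% at full hazard, in the scenarios tabulated above. Over a wider set (Swiss share 25-100%, either end date, late hazard 10-100% of design) the figure is 1-25% if events after the last call are also counted, so the number at risk should be shown beside the late curve. The month-60 cut brings this below 1% but drops on average 0.06-3.3 late events over that wider set.
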